7.1 Type of study

This is a monocentric retro-prospective observational study. Patients were already treated since many years before the beginning of the study.

7.3 Study timelines

Total duration: **13 days**

Duration of the inclusion period: considering that all patients have already been treated, therefore, there's no inclusion period. Potential

Duration of the follow-up period for each patient: 10 years

Study start (estimated): **November 2019**

Recruitment end: Not applicable

End of the patient follow-up period (estimated): September **November 2019**

Data analysis period (estimated): **Q1 2020**

End of the study (estimated): **Q1 2020**

8 Study population

8.1 Sample size

The sample size was arbitrarily chosen to have a cohort of consecutive patients to have the strongest power in

| | | | |
|---|------------------------------|---|--|
|  OSERF | Document No. | SAGITTA EVL-R STEMS – NOVAE / SAGITTA EVL-R CUPS | ID RCB : 2019-A01777-50 |
| | 2019-10-EVLR-N Version 02 | | Page No. Page 18 sur 28 |

such type of study and by limiting exclusion criteria. Only contraindications of the IFU were taken as exclusion criteria. In that way, a cohort of 120 consecutive patients was defined to have a basis of calculation.

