Number of needed patients:

The number of needed patients was determined arbitrarily and is based on an estimated sufficient number to have a real incidence when means will be calculated.

→Number of patients in the cohort: 120

| | |
|-----------------------|---|
| Collected data | 
Preoperative phase:
 
Sociodemographic data: age, sex, weight, height
 
Medical & surgical history, risk factors and comorbidities
 
Primary diagnosis and operative indication.
 
Daily physical activities
 
Charnley Classification
 
Operative & immediate postoperative phases :
 
Perioperative & immediate postoperative complications;
 
Surgery description (assembly of components and sizes, description of the devices used in combination with Sagitta EVL-R stems);
 
Immediate postoperative radiologic evaluation;
 
Post-operative data (6 months, 1, 2, 5, and potentially between 5 to 8 years):
 
Radiologic evaluation (inclination of the cup, localization of the rotation center, presence of periprosthetic radiolucent line for the cup and the stem, height of the stem comparing with an anatomic locator)
 
Postoperative data through unique individual phone call corresponding to 5 to 8 postoperative years:
 
 - Oxford clinical scores - Daily physical activities - Global outcomes: Patient's satisfaction, walking ability, functional improvement, |
|-----------------------|---|

| | | | |
|---|--------------------------------|---|-------------------------------|
|  | Document No. 2019-10-EVLR-N | SAGITTA EVL-R STEMS – NOVAE / SAGITTA EVL-R CUPS | ID RCB : 2019-A01777-50 |
| | Version 02 | | Page No. Page 8 sur 28 |

release pain
- Charnley Classification

Postoperative complications all over the follow-up of patients between the preoperative period until the phone call (5 to 8 years)

| | | | |
|--|----------------------------------|---|---|
|  serf | Document No. | SAGITTA EVL-R STEMS – NOVAE / SAGITTA EVL-R CUPS | ID RCB : 2019-A01777-50 |
| | 2019-10-EVLR-N Version 02 | | |
| | | | Page No. Page 9 sur 28 |

ABBREVIATIONS

| | |
|-------------|---|
| AAOS | American Academy of Orthopaedic Surgeons |
| ADE | Adverse device Effect |
| AE | Adverse Event |
| BMI | Body Mass Index |
| CRF | Case Report Form |
| HAS | Haute Autorité de Santé |
| HHS | Harris Hip Score |
| NICE | National Clinical Guideline Centre |
| OHS | Oxford Hip Score |
| SAE | Serious Adverse Event |

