For acute pathologies such as fractures, the treatment is surgical with total hip replacement as mentioned in recommendations (AAOS and NICE) (Brown 2017; « NICE - 2017 - Hip fracture management Guidance and guidelines.pdf » 2017).

Considering principal method of surgical strategies, risk factors appear for revision procedure. Moerman et al. have studied the Dutch arthroplasty registry. They have found a revision rate in hemiarthroplasty (HA) of 1.6% at 1 year and 2.5% at 5 years postoperatively. In total Hip Arthroplasty (THA), the rate was 2.4% at 1 year and

| | | | |
|---|------------------------------|---|--------------------------------|
|  | Document No. | SAGITTA EVL-R STEMS – NOVAE / SAGITTA EVL-R CUPS | ID RCB : 2019-A01777-50 |
| | 2019-10-EVLR-N Version 02 | | Page No. Page 11 sur 28 |

4.3% at 5 years postoperatively (Moerman et al. 2018). They have also analyzed that risk factors for hemiarthroplasty were male sex, age below 80 years, a posterolateral approach and uncemented fixation. Risk factors following THA were exactly the same with smoking in addition. To be noted that the age as a risk factor for revision is not a risk factor for revision in the first year after the fracture but becomes one in the years thereafter (Moerman et al. 2018). Whatever the primary or the revision uses, these stems are used mainly due to the encountered pathologies and the need for the supplemental fixations with distal screws.

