13.2 Statistical analysis

The data will be analyzed using an excel Microsoft office 2016. All data will be expressed qualitatively and/or quantitatively (frequency and/or percentage). All data will finally be compared to those found in the bibliography.

The previous section includes the main elements of the statistical analysis plan. This plan may be revised to reflect any modifications to the protocol. Any such revisions will be made before freezing the database.

Statistical analysis will be performed in SERF's facilities.

14 Quality assurance

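### Section 8.1 claims the strongest power for an arbitrary 120 patients, but no hypothesis is stated, so no power exists, and 120 gives wide intervals for the secondary failure rates

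*Protocol*

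**What the plan says.** Section 8.1 gives the basis of the sample size: "The sample size was arbitrarily chosen to have a cohort of consecutive patients to have the strongest power in" such a study, helped by keeping exclusion criteria few. It adds that "a cohort of 120 consecutive patients was defined to have a basis of calculation", and that contraindications in the instructions for use are the only exclusion criteria.

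The Summary (section 1, number of needed patients) also calls the number arbitrary but gives another reason: it was "determined arbitrarily and is based on an estimated sufficient number to have a real incidence when means will be calculated".

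Section 7.1 fixes the design: "This is a monocentric retro-prospective observational study". There is no control arm.

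Section 13.2 gives the analysis: "All data will be expressed qualitatively and/or quantitatively (frequency and/or percentage"), and then "All data will finally be compared to those found in the bibliography".

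The primary endpoint is the Oxford Hip Score, from 12 to 60 points (section 6.3). Table 1 in section 10 shows it collected only at the phone call. Survival, aseptic loosening and complication rates are secondary (section 6.2).

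**The concern.** Section 8.1 credits the design with a statistical property that nothing in the protocol supports. An arbitrary number cannot also have been chosen to maximise power, and without a hypothesis there is no power to maximise. The two reasons given for 120 also differ: one appeals to power, the other to calculating means, while section 13.2 names frequencies and percentages.

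The wording matters because of how the results will be used. Section 16.1 intends them mainly as proof of performance and safety in the claimed indications, and also for marketing, and section 13.2 judges them against published figures. If a failure rate close to a published one comes with a claim of strongest power, it may be read as evidence of equal safety when the interval around it is wide.

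The cohort description in section 8.1 is also too simple. Section 8.2 requires at least 24 months of follow-up and non-opposition, and section 8.5 allows removal after inclusion when 24-month data are too poor. These conditions bear on whether the cohort is truly consecutive.

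**Working it through.** **1. Can 120 be reproduced?** No. The protocol gives no null value, alternative, alpha, sidedness, target power, SD, margin, precision target or loss allowance. There is nothing to enter in a sample-size formula, and no power can be computed.

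**2. Precision for failure rates (exact Clopper-Pearson 95% intervals).** With 0 events in n, the upper limit is 1 − 0.025^(1/n). For n = 120 this is 1 − 0.025^(1/120) = 3.0%.

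| Events / n | Rate | 95% interval |
|---|---|---|
| 0/120 | 0% | 0 to 3.0% |
| 3/120 | 2.5% | 0.5 to 7.1% |
| 5/120 | 4.2% | 1.4 to 9.5% |
| 3/72 (assumes 60% evaluable) | 4.2% | 0.9 to 11.7% |

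Five events in 120 is the whole-number count nearest to the 5-year revision rate for total hip arthroplasty quoted in section 3.1, "4.3% at 5 years postoperatively". The interval runs from about one third of that rate (1.4/4.3 = 0.33) to more than twice it (9.5/4.3 = 2.2). A half-width of 2 points at 4.3% would need 1.96² × 0.043 × 0.957 / 0.02² ≈ 396 patients (normal approximation).

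**3. Illustrative test only.** The protocol sets no test, and 4.3% is a background registry rate. Let X be binomial with n = 120 and null 4.3% (120 × 0.043 = 5.2 expected events). The alternative is a doubling to 8.6%.

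| One-sided exact level | Reject if | Actual size | Probability of detection at 8.6% |
|---|---|---|---|
| 2.5% | X ≥ 11 | 1.5% | 45.9% |
| 5% | X ≥ 10 | 3.5% | 58.9% |

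**4. Precision for the primary endpoint.** The 95% half-width of a mean is 1.96 × SD/√n. The protocol gives no SD, so a range of 8 to 12 points is assumed.

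| n | Half-width | At SD 8 to 12 |
|---|---|---|
| 120 | 1.96/√120 = 0.18 SD | 1.4 to 2.1 points |
| 96 (assumes 80% reached) | 1.96/√96 = 0.20 SD | 1.6 to 2.4 points |
| 72 (assumes 60% reached) | 1.96/√72 = 0.23 SD | 1.8 to 2.8 points |

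On a 48-point range this is fairly tight.

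**5. Who are the 120?** Section 8.4 makes inclusion definitive at the assessment of the electronic file. Section 15.1 has the patient agree orally, at the phone call, to be included, after which the questionnaire starts. Under section 8.4, anyone not reached is included but has no Oxford score. Under section 15.1, all 120 are reached patients, but the cohort is then consecutive only among those who could be reached and did not object. The two sections must be reconciled before the number contributing to the primary endpoint is known.

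**The case against.** The best defence is that a descriptive, single-arm post-market cohort needs no power calculation, and that the protocol openly calls its number arbitrary in two places. The sentence in section 8.1 is relative to this type of study, claims no numerical power, and may use the word loosely for evidential strength. All of this stands as regards the missing calculation, which is not the complaint. It does not rescue the sentence: even read loosely, consecutive enrolment and few exclusions protect against selection bias and do not create power.

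Four stronger readings are tempting, and the protocol does not support them.

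- **That 120 has been shown to be too few.** This needs a null value and a test, and the protocol has neither. The 4.3% follows a sentence on fractures in section 3.1, whereas section 6 says these stems serve mainly for revision of arthroplasties. The 46 to 59% shows scale and no more.
- **That the primary endpoint is imprecise.** The half-width of a proportion near 50% is 8.9 percentage points at n = 120 and 11.5 at n = 72. Those figures do not apply to the mean of a 12-to-60 score. The largest SD possible on that range is 24, so even at n = 72 the half-width cannot exceed 0.23 × 24 ≈ 5.5 points.
- **That fewer than 120 patients will have a primary outcome.** Sections 8.4 and 15.1 conflict, so this is open.
- **That section 13.2 rules out means or intervals.** It says results may be expressed quantitatively, and a separate analysis plan, not seen here, may give more detail.

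**Conclusion.** Wrong as written. Section 8.1 asserts a power that cannot exist, because the protocol states no hypothesis, null value, effect or precision target.

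The practical harm is confined to the secondary rates. With 120 patients, a failure rate that looks like a published one remains compatible with a rate more than twice as high: 5/120 has an upper limit of 9.5%. Zero events would still not exclude 3.0%. These intervals rest only on n = 120 and exact binomial limits. The detection probabilities rest in addition on a borrowed null value and a chosen alpha.

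The mean Oxford Hip Score is not affected in the same way. Its half-width is about 0.18 SD at 120, and 0.23 SD if only 72 are reached. The SD and the number reached are assumptions, since the protocol gives neither.

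**What to change.** 1. **Section 8.1 and Summary.** Delete the claim of strongest power and the phrase "based on an estimated sufficient number to have a real incidence when means will be calculated". State that 120 is a feasibility number and that no hypothesis is tested.
2. **Precision.** State the expected 95% precision for failure rates and for the mean Oxford score, at 120 and at the number of phone responders the sponsor expects. The tables above can be used once the sponsor supplies its own SD and contact rate.
3. **Section 13.2.** Require a 95% confidence interval with every rate and mean set against the literature, and say that a similar point estimate is not proof of equal safety.
4. **Sections 8.4 and 15.1.** Reconcile them on when a patient counts as included, and give the denominator for the phone-call outcomes accordingly.
5. **Consecutive cohort.** Keep the term only if every EVL-R implantation from 2011 to 2014 is listed with the reason for any exclusion: the 24-month minimum, objection, or not reached. Bring the statement on exclusion criteria in section 8.1 into line with sections 8.2 and 8.5.

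The cost is small: rewording, a list drawn from existing files and slight extra analysis, with no additional patients. The downside for the sponsor is a less favourable statement about what the study can show on safety.

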8.2 Inclusion criteria

The inclusion and exclusion criteria are controlling legal aspects of a clinical study in general; and the respect of indications cited in the instruction for use of the medical device. There's no other imposed restrictions.

The inclusion criteria are:

- Patients over 18 years old.
- Patients that were treated for an indication of arthroplasty and according to the Instruction For Use (IFU).
 - Primary or secondary arthrosis,
 - Advanced joint destruction resulting from rheumatoid arthritis or traumatic arthritis,
 - A fracture or an avascular necrosis,
 - Following a previous surgical operation, on condition that the new device does not interfere with the material in place.
 - indicated in the case of primary or secondary arthrosis, displaced sub-capital or transcervical fracture as well as stages I and IIB bone loss according to the PAPROWSKI classification.
 - The SAGITTA EVOLUTION for REVISION implant is recommended for indications according to the bone loss classifications of SOFCOT stages I to VI, PAPROSKY types I to VI and the AAOS types Ia to Ic.
 - Dysplasia
- Patient being informed to the study and non-opposed of its participation and the use its pertaining data.
- Patients with a minimum follow up of 24 months.

8.3 Non-inclusion criteria

The Non-inclusion criteria are:

- Patient presenting a contraindication indicated in the IFU.

8.4 Definitive inclusion

A patient is definitely included in the study if declared eligible during the electronic file assessment.

8.5 Exclusion criteria

After inclusion, patients can be excluded from the study if the final follow up is 24 months and if available data at the 24 months postoperative visit is too poor.

9 Study procedures

Patient information:

This observational study does not require any additional eligibility criteria, any additional exam. According to French regulation, each patient is appropriately informed of his/her freedom to decline or agree to participate to the study (thanks to the information note) and of his rights regarding medical data collection.

Study withdrawal:

Patients may withdraw from the study at any time at their own request, or they may be withdrawn at any time at the discretion of the investigator or sponsor for safety, behavioral, or administrative reasons. In any circumstance, every effort should be made to document patient outcome, if possible.

| | | | | | |
|--|----------------|---|-------------------------|----------------|--|
|  serf | Document No. | SAGITTA EVL-R STEMS – NOVAE / SAGITTA EVL-R CUPS | ID RCB : 2019-A01777-50 | | |
| | 2019-10-EVLR-N | | Page No. | Page 19 sur 28 | |

10 Collected data

Patients will be followed at 2 stages: in their medical history files and through a phone call [after](#) the surgery.

| Endpoints | Preoperative | Per-operative | Immediate post-operative | Visit 6 months | Visit 1 year | Visit 2 years | Last visit over 2 years | Phone call to patients |
|--|---|---------------|--------------------------|----------------|--------------|---------------|-------------------------|------------------------|
| Patient information (gender, age, weight, height) | X | | | | | | | |
| Eligibility criteria | X | | | | | | | |
| Medical & surgical history | X | | | | | | | |
| Oxford questionnaires | | | | | | | | X |
| Daily physical activity | | | | | | | | X |
| Charnley Classification | X | | | X | X | X | X | X |
| Surgery - Assembly components description | | X | | | | | | |
| Peroperative Incidents | | X | | | | | | |
| Global results: Patient satisfaction Walking ability Functional improvement Pain release | | | | | | | | X |
| Length of the operated limb | | | | | | | | X |
| Radiologic assessment | Inclinaison of the Cup and localization of the center of rotation | | X | X | X | X | X | X |
| | Periprosthetic radiolucent line - Cup | | X | X | X | X | X | X |
| | Stem height/ anatomic locator | | X | X | X | X | X | X |
| | Periprosthetic radiolucent line - stem | | X | X | X | X | X | X |
| Complications (including implant migration, iterative dislocation, aseptic loosening, breakage...) | | X | X | X | X | X | X | X |

Table 1: Collected data and study timelines

| | | | |
|--|------------------------------|---|--|
|  serf | Document No. | SAGITTA EVL-R STEMS – NOVAE / SAGITTA EVL-R CUPS | ID RCB : 2019-A01777-50 |
| | 2019-10-EVLR-N Version 02 | | Page No. Page 20 sur 28 |

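### Section 8.5 allows an included patient to be dropped for poor 24-month data, with no threshold, against 8.1 and 8.2; survival and complication rates become selected on documentation

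*Protocol*

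**What the plan says.** Four statements in section 8 of the protocol bear on who stays in the cohort.

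- Section 8.1: "Only contraindications of the IFU were taken as exclusion criteria", and "a cohort of 120 consecutive patients was defined to have a basis of calculation".
- Section 8.2: the criteria cover legal aspects and the indications in the instructions for use, and then "There's no other imposed restrictions". The list that follows nevertheless ends with "Patients with a minimum follow up of 24 months".
- Section 8.4: "A patient is definitely included in the study if declared eligible during the electronic file assessment".
- Section 8.5: "After inclusion, patients can be excluded from the study if the final follow up is 24 months and if available data" at that visit are inadequate. The exact condition is "if available data at the 24 months postoperative visit is too poor".

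Section 8.5 does not list the items that must be present, set a level of completeness, or say who decides. Section 6.2 undertakes to record all complications and to calculate survival at each timepoint, an aseptic loosening rate and a global complication rate. Table 1 in section 10 collects complications from the operation onwards, including at 6 months and 1 year.

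**The concern.** Section 8.5 acts on the patient, although the problem it addresses lies in one visit. A thin 24-month record does not invalidate an operative complication or a 1-year film already taken from the same file. If the patient leaves the study, those data leave with the visit.

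The trigger is completeness of data, which is neither a legal criterion nor one from the instructions for use, so 8.1 and 8.2 cannot both stand as written beside 8.5. Because the threshold is undefined, nothing in the text prevents a removal that depends on outcome. The rates at stake are those that section 13.2 compares with the literature and that section 16.1 intends mainly as evidence of performance and safety. A series thinned in this way is no longer the consecutive one described in 8.1.

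**Working it through.** **No stated figure to reproduce.** Section 8.1 calls the cohort size arbitrary and gives no error rate, power, effect size or dropout. The check is a comparison of rules, followed by an illustration of scale.

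**Comparison of rules**

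1. 8.1 against 8.5. Both use the term exclusion criteria. 8.1 allows one kind only, contraindications in the instructions for use. 8.5 adds another, poor data at 24 months. They conflict.
2. 8.2 against 8.5. 8.2 says that its criteria, and the exclusion criteria with them, impose nothing beyond legal aspects and the instructions for use. 8.5 does impose something more. They conflict.
3. 6.2 against 8.5. 6.2 promises rates over all recorded complications. No passage keeps a patient excluded under 8.5 in those rates. The sentence in section 9 about documenting outcomes concerns withdrawal and sets no denominator.
4. Reach of 8.5. Both conditions must hold: final follow-up at 24 months and poor data at that visit. Patients with less than 24 months of follow-up are already removed by 8.2 and never reach 8.5.

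**Scale, illustration A (all inputs except 120 are assumed)**

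Let N = 120 patients, E = 8 failures, k = 10 patients removed and j = failures among those removed. The reported rate is (E − j)/(N − k).

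- No removal: 8/120 = 6.7%.
- k = 10, j = 3: (8 − 3)/(120 − 10) = 5/110 = 4.5%.
- k = 10, j = 0: 8/110 = 7.3%.
- Share of the denominator lost: 10/120 = 8.3%.

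The rate is unchanged only if the removed patients fail at the overall rate, that is, if j = 10 × 8/120 = 0.67. With no failures among the ten the rate rises; with one or more it falls.

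**Scale, illustration B (event rate taken from the protocol)**

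Section 3.1 cites a registry revision rate of 4.3% at 5 years for total hip arthroplasty. 0.043 × 120 = 5.16, or about 5 events. The number removed is an assumption, from 6 to 24. Intervals are exact (Clopper-Pearson) 95% intervals.

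| Removed | Events among them | Rate | 95% interval |
|---|---|---|---|
| 0 | 0 | 5/120 = 4.2% | 1.4 to 9.5% |
| 6 | 2 | 3/114 = 2.6% | 0.6 to 7.5% |
| 12 | 0 | 5/108 = 4.6% | 1.5 to 10.5% |
| 12 | 2 | 3/108 = 2.8% | 0.6 to 7.9% |
| 12 | 3 | 2/108 = 1.9% | 0.2 to 6.5% |
| 24 | 2 | 3/96 = 3.1% | 0.7 to 8.9% |

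With so few events, two or three discretionary removals shift the point estimate by a third to a half of its value. The intervals overlap widely throughout.

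**The case against.** **The rule is narrow, and its main mechanism lies elsewhere.** Patients who died or were lost before 24 months are removed by the entry criterion in 8.2. Deleting 8.5 would not bring them back or restore a consecutive series. This stands, and it limits the point to a subset of unknown size.

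**Included patients may all have later contact.** Section 8.2 requires non-opposition, and section 15.1 obtains it in the phone call. On that reading an included patient has been reached at 5 to 8 years, and a final follow-up of 24 months can only mean the last visit on file. Section 8.4 instead fixes inclusion at the file assessment. The documents leave this open, so a reader should not infer that 8.5 concerns only patients with no later contact.

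**8.5 contradicts 8.4.** A reader might infer this from the word definitely in 8.4, but the documents do not support it. 8.5 begins after inclusion and so follows 8.4 in sequence.

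**8.1 may only be loosely worded.** Its exclusion criterion matches the non-inclusion criterion of 8.3, so it may have meant entry restrictions. That is possible, but 8.1 and 8.5 use the same term, 8.2 reinforces 8.1, and the text still has to be reconciled.

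**The loss from the rates is inferred.** The protocol defines no analysis set, and an analysis plan that is not shown might do so. It is also not stated that whoever judges the file has its complications in view. Both are fair limits. Exclusion from the study is nevertheless the plain wording, and section 13.2 says that the protocol already holds the main elements of the analysis plan.

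**The bias flatters the device.** This is tempting, because poorly documented patients could include deaths or revisions elsewhere, but the documents give no evidence for it. Illustration A rises to 7.3% when no failures are removed.

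**Conclusion.** The point holds as a conflict between 8.5 and sections 8.1 and 8.2, and as a badly fixed rule: a patient-level exclusion on data completeness, with no threshold, in a series described as consecutive. Read plainly, it drops valid earlier data and leaves the survival, loosening and complication rates selected on documentation.

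Its size cannot be derived from the documents. Under illustration A the failure rate could move from 6.7% to 4.5% or to 7.3%; under illustration B, with 12 removed, from 4.2% to between 1.9% and 4.6%. The numbers removed and the events among them are assumptions, and the direction is not fixed.

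Only secondary results are materially exposed. The Oxford Hip Score is collected only at the phone call, so a patient whose follow-up truly ends at 24 months has no score to lose. A score could be lost only if final follow-up means the last clinic visit. The point merits correction, but it does not undermine the primary endpoint.

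**What to change.** 1. Delete the patient-level exclusion in 8.5.
2. Keep every included, non-opposed patient in the survival and complication analyses for the period with data, and censor implant survival at last contact.
3. Treat a poor 24-month item, such as an unreadable film, as missing for that item and visit only, and report missing data by item and visit.
4. Reconcile 8.1 and 8.2 with the result. State openly there that the 24-month entry criterion in 8.2 is itself a restriction that selects on follow-up; this change does not remove it.

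If the sponsor prefers to keep a completeness rule for patients, the minimum is to define it by listed items and to report the number excluded with reasons. That would make the selection visible but would not remove it.

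The cost is one deleted sentence and a short statement on handling, with no extra patients or data collection. The 24-month tables will show more missing cells, and the reported rates may move in either direction.
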